6.5.2 Dose modification and toxicity management for cetuximab

Cetuximab should be reduced, delayed, or discontinued to manage adverse reactions as described in [Table 6.3](#).

Table 6.3: Recommended dose modifications of cetuximab for adverse reactions

Adverse reaction	Severity (CTCAE, version 5.0)	Dose modification
Infusion reactions	Grade 1	Reduce the infusion rate by 50%. Infuse under close supervision.
	Grade 2	Reduce the infusion rate by 50%. Immediately administer treatment for symptoms.
	Grade 3 or 4	Immediately stop infusion and permanently discontinue cetuximab.
Dermatologic toxicities and infectious sequelae (e.g., acneiform rash,	First occurrence; grade 3 or 4	Delay infusion 1 to 2 weeks; if condition improves to grade ≤ 2 , continue at 250 mg/m^2 . If no improvement, discontinue cetuximab permanently.

Adverse reaction	Severity (CTCAE, version 5.0)	Dose modification
mucocutaneous disease)	Second occurrence; grade 3 or 4	Delay infusion 1 to 2 weeks; if condition improves to grade ≤ 2 , continue at 200 mg/m^2 . If no improvement, discontinue cetuximab permanently.
	Third occurrence; grade 3 or 4	Delay infusion 1 to 2 weeks; if condition improves to grade ≤ 2 , continue at 150 mg/m^2 . If no improvement, discontinue cetuximab permanently.
	Fourth occurrence; grade 3 or 4	Discontinue cetuximab permanently.
Pulmonary toxicity	Acute onset or worsening pulmonary symptoms	Delay infusion 1 to 2 weeks; if condition improves, continue at the dose that was being administered at the time of occurrence. If no improvement in 2 weeks or interstitial lung disease is confirmed, discontinue cetuximab permanently.
Ulcerative keratitis	Confirmed diagnosis	Interrupt or discontinue cetuximab permanently.

6.5.3 Clinical management of cytokine release syndrome

Symptoms of cytokine release will be managed as per [Table 6.4](#) and according to local standard practice and in line with published guidelines.^{22,23}

Recommendations for cytokine release syndrome management described in [Table 6.4](#) can be modified by the individual study center as medically necessary or as appropriate without requiring a Protocol Amendment or being considered a Protocol deviation.

Table 6.4: Clinical management of cytokine release syndrome²⁴

Grading assessment	Treatment
Grade 1 • Fever, constitutional symptoms	
 • Vigilant supportive care • Assess for infections

Grading assessment	Treatment
	(Treat fever and neutropenia if present, monitor fluid balance, antipyretics, analgesics as needed)
Grade 2 
 • Hypotension: responds to fluids or one low dose pressor • Hypoxia: responds to <40% O₂ • Organ toxicity: grade 2 	Extensive comorbidities or older age? 
 → No: Vigilant supportive care (Monitor cardiac and other organ function closely) → Yes: Vigilant supportive care Tocilizumab* ± corticosteroids
Grade 3 
 • Hypotension: requires multiple pressors or high dose pressors • Hypoxia: requires ≥40% O₂ • Organ toxicity: grade 3, grade 4 transaminitis 	
 • Vigilant supportive care • Tocilizumab* ± corticosteroids
Grade 4 
 • Mechanical ventilation • Organ toxicity: grade 4, excluding transaminitis 	
 • Vigilant supportive care • Tocilizumab* ± corticosteroids

*Should be used if no other treatment option, only

6.5.4 Additional diagnostic measurements

Patients with pre-existing pulmonary diseases and patients taking concomitant chemotherapy known to be associated with interstitial lung disease (ILD) should be closely monitored. In the event of symptoms (such as dyspnoea, cough, fever) or radiographic findings suggestive of ILD, prompt diagnostic investigation should occur. If interstitial lung disease is diagnosed, cetuximab must be discontinued and the patient be treated appropriately.

Patients presenting with signs and symptoms suggestive of keratitis such as acute or worsening: eye inflammation, lacrimation, light sensitivity, blurred vision, eye pain and/or red eye should be referred promptly to an ophthalmology specialist. If a diagnosis of ulcerative keratitis is confirmed, treatment with cetuximab should be interrupted or discontinued. If keratitis is diagnosed, the benefits and risks of continuing treatment should be carefully considered. Cetuximab should be used with caution in patients with a history of keratitis, ulcerative keratitis or severe dry eye. Contact lens use is also a risk factor for keratitis and ulceration.

6.6 Continued access to study intervention after the end of the study

Further supply of nanrilkefusp alfa beyond study completion will be ensured by the sponsor in case the investigator considers continued treatment with nanrilkefusp alfa as beneficial.

6.7 Treatment of overdose

For this study, an overdose of nanrilkefusp alfa will be defined as any dose above 13 µg/kg.

For this study, an overdose of cetuximab will be defined as any dose above 120% of the planned dose (i.e., 480 mg/m² for the initial dose and 300 mg/m² for subsequent doses).

No specific information is available on the treatment of overdose of nanrilkefusp alfa and/or cetuximab. In the event of overdose, the patient should be observed closely for signs of toxicity. Appropriate supportive treatment should be provided if clinically indicated.

6.8 Concomitant therapy

All treatments that the investigator considers necessary for a patient's welfare may be administered at the discretion of the investigator in keeping with the community standards of medical care.

All concomitant medication will be recorded on the electronic Case Report Form (eCRF) including all prescription and over-the-counter products, herbal supplements, and intravenous medications and fluids. If changes occur during the study period, documentation of drug dosage, frequency, route, and date should also be included on the eCRF.

All concomitant medications received from ICF signature to 90 days after the last dose of nanrilkefusp alfa and/or cetuximab (whichever occurs later) should be recorded. All concomitant medications administered during (S)AEs are to be recorded. SAEs are defined in section 8.3.1.2.

6.8.1 Rescue medication and supportive care

Patients should receive appropriate supportive care measures as deemed necessary by the treating investigator.

6.8.2 Prohibited medications

If there is a clinical indication for any medication or vaccination specifically prohibited during the trial, discontinuation from study interventions may be required (also see section 7.1). The investigator is to discuss prohibited medication/vaccination with the sponsor's medical monitor. The final decision on any supportive therapy or vaccination rests with the investigator and/or the patient's primary physician. However, the decision to continue the patient on study interventions requires the mutual agreement of the investigator, the sponsor, and the patient.

Listed below are specific restrictions for concomitant therapy or vaccination during the course of the study:

- Concomitant use of drugs known to prolong the QT/QTc interval during the study should be avoided and only should be used if clinically indicated and in case of no other alternative. Some of the medications known to prolong the QT interval are²⁵ amiodarone, azithromycin, ciprofloxacin, chlorpromazine, citalopram, domperidone, donepezil, escitalopram, fluconazole, haloperidol, levofloxacin, levomepromazine, methadone,

ondansetron, and sulpiride. A complete list of medications known to prolong the QT interval can be found at www.crediblemeds.org.

- Administration of live or live-attenuated vaccines within 30 days prior to the first dose of study interventions and within 90 days after the last dose of nanrilkefusp alfa and/or cetuximab, whichever is later, is prohibited. Note: Killed vaccines are allowed.
- Administration of another study intervention during treatment with nanrilkefusp alfa and cetuximab is prohibited.
- Another anti-cancer therapy during treatment with nanrilkefusp alfa and cetuximab is prohibited. Palliative radiotherapy of, e.g., painful bone metastases not defined as indicator lesions is allowed.

7 DISCONTINUATION OF STUDY INTERVENTION AND PATIENT DISCONTINUATION/WITHDRAWAL

7.1 Discontinuation of study intervention

Discontinuation of study treatment does not represent withdrawal from the study.

A patient must be discontinued from study treatment for any of the following reasons:

- Confirmed radiographic disease progression as specified in section [10.2.7](#).
- Clinical disease progression (investigator's assessment)
- AE, namely intercurrent illness or study treatment-related toxicity that would, in the judgment of the investigator, affect assessments of the patient's clinical status to a significant degree or require discontinuation of study treatments
- Pregnancy of the patient
- Concomitant treatment with a prohibited medication
- Initiation of new systemic anti-cancer therapy
- Patient's decision
- Investigator's decision

After discontinuation of nanrilkefusp alfa and/or cetuximab (whichever occurs later), all patients will be followed up in the study as described in section [4.1.4.3](#).

If nanrilkefusp alfa needs to be stopped, patients will discontinue cetuximab as well. Such patients will receive standard of care treatment outside the clinical trial.

If cetuximab needs to be stopped due to an AE or the patient's or investigator's decision, nanrilkefusp alfa treatment can continue until any of the criteria for stopping or discontinuation of study treatment listed above is met. If cetuximab needs to be stopped for any of the reasons listed above except for an AE or the patient's or investigator's decision, nanrilkefusp alfa needs to be discontinued as well.

7.2 Patient discontinuation/withdrawal from the study

A patient may withdraw from the study at any time at his/her own request or may be withdrawn at any time at the discretion of the investigator for safety, behavioral, compliance, or administrative reasons, or when the study is discontinued by the sponsor. This is expected to be uncommon. The patient will be permanently discontinued both from the study interventions and from the study at that time.

If the patient withdraws consent for disclosure of future information, the sponsor may retain and continue to use any data collected before such a withdrawal of consent.

If a patient withdraws from the study, s/he may request destruction of any samples taken and not tested, and the investigator must document this in the site study records.

7.3 Lost to follow-up

A patient will be considered lost to follow-up if s/he repeatedly fails to return for scheduled visits and is unable to be contacted by the study site.

The following actions must be taken if a patient fails to return to the clinic for a required study visit:

- The site must attempt to contact the patient and reschedule the missed visit as soon as possible and counsel the patient on the importance of maintaining the assigned visit schedule and ascertain whether or not the patient wishes to and/or should continue in the study.
- Before a patient is deemed lost to follow-up, the investigator or designee must make every effort to regain contact with the patient (where possible, 3 telephone calls and, if necessary, a certified letter to the patient's last known mailing address or local equivalent methods). These contact attempts should be documented in the patient's medical record.
- Should the patient continue to be unreachable, s/he will be considered to have withdrawn from the study.

8 STUDY ASSESSMENTS AND PROCEDURES

Study procedures and their timing are summarized in the [Schedule of activities](#). Protocol waivers or exemptions are not allowed.

Immediate safety concerns should be discussed with the sponsor immediately upon occurrence or awareness to determine if the patient should continue or discontinue study interventions.

Adherence to the study design requirements, including those specified in the [Schedule of activities](#), is essential and required for study conduct.

All screening evaluations must be completed and reviewed to confirm that potential patients meet all eligibility criteria. The investigator will maintain a screening log to record details of all patients screened and to confirm eligibility or record reasons for screening failure, as applicable.

RAS wild type at screening will be determined by using a locally performed FDA-approved test or an experienced local laboratory using validated test methods for the detection, based on tumor biopsy, or locally performed ctDNA assessment (including at least mutations in exon 2 [G12D, G12V, G12C, G12S, G12A, G12R, G13D]), determined by a laboratory using validated test methods. FDA-approved tests are listed here: <https://www.fda.gov/medical-devices/in-vitro-diagnostics/list-cleared-or-approved-companion-diagnostic-devices-in-vitro-and-imaging-tools>.

Procedures conducted as part of the patient's routine clinical management and obtained before signing of the ICF may be utilized for screening or baseline purposes provided the procedures met the Protocol-specified criteria and were performed within the time frame defined in the [Schedule of activities](#).

8.1 Efficacy assessments

Throughout this section, the term "scan" refers to any medical imaging data used to assess tumor burden and may include cross-sectional imaging (such as CT or MRI), medical photography, or other methods as specified in this Protocol except ultrasound which is unacceptable for efficacy assessments.

Scan evaluation by a local radiologist or by the investigator will be used for the main analyses. However, all scheduled scans for patients will be collected. In case of a deemed need for health authority interactions, a sensitivity analysis will be considered based on evaluation of imaging documentation by an independent review committee. A scan that is obtained at an unscheduled time point, for any reason (including suspicion of progression or other clinical reason), will also be collected if it shows disease progression, or if it is used to support a response assessment. In addition, historical scans that were obtained at disease progression on previous systemic anti-cancer treatment will be collected and may be qualified by an independent review committee.

The process for scan collection can be found in the site imaging manual. CT scans are preferred over other tumor imaging methods. For the abdomen and pelvis, contrast-enhanced MRI may be used when CT with iodinated contrast is contraindicated, or when mandated by local practice. The same type of scan should be used in a patient throughout the study to optimize the reproducibility of the assessment of existing and new tumor burden and improve the accuracy of the assessment of response or progression based on imaging. Note: for the purposes

of assessing tumor scans, the term “investigator” refers to the local investigator at the site and/or the radiologist located at the site or at an offsite facility.

If brain scans are performed, magnetic resonance scans are preferred; however, CT scans are acceptable if MRI is medically contraindicated.

Bone metastases should be assessed using an adequate method (e.g., bone scans).

8.1.1 Initial tumor scans

Initial tumor scans must be performed within 21 days prior to ICF signature. The site study team must review screening scans to confirm the patient has measurable disease per RECIST 1.1.

If brain scans are performed to document the stability of existing metastases, the brain MRI should be acquired during screening. If MRI is medically contraindicated, CT with contrast is an acceptable alternative.

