	
case of a confirmed response or disease progression, the date of the first tumor assessment evaluated as response or progression will be used for the time-to-event variables.
 
The last value of CT scan or MRI on or up to 21 days before the date of the first study treatment will be used as the baseline value for each assessment. Only tumor assessments prior to or at the date of initiation of further-line therapy and using CT scan or MRI will be used for the evaluation of tumor response.

Internal safety committee	
Applicable only to the safety cohorts: An internal safety committee (ISC) will be established for the safety cohorts of this study to evaluate patients' safety. The ISC will be tasked with making decisions based on their review to continue, modify, or stop recruitment or the trial based on their assessment of the safety data. The membership, key responsibilities, and the corresponding procedures will be defined in the ISC Charter.

Independent data monitoring committee	
Applicable only to the main cohort: An independent data monitoring committee (IDMC) will be established for the main cohort to safeguard the interest and safety of the patients participating in the study and provide independent review and assessment of the efficacy and safety data in a systematic manner.
 
The IDMC will be tasked with making a recommendation to the sponsor based on their review to continue, modify, or stop recruitment or the trial based on their assessment of efficacy and safety information. The membership, key responsibilities, and the corresponding procedures will be defined in the IDMC Charter.

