1.3 Schedule of activities

Cycle	Visit	Screening Up to 21 days before day 1 of cycle 1	Cycle 1					From cycle 2 onwards				End of treatment* Within 7 (+7) days after the last dose of nanrilkefusp alfa and/or cetuximab (whichever occurs later)	Follow -up	
			Day 1	Day 2 (±1 day)	Day 8 (±1 day)	Day 9 (±1 day)	Day 15 (±1 day)	Day 1 (±1 day)	Day 2 (±1 day)	Day 8 (±1 day)	Day 9 (±1 day)	Day 15 (±1 day)		
Informed consent¹	X													
Demography²	X													
Cancer³ and medical history	X													
K-RAS/N-RAS	X		Optional at disease progression											
Body height	X													
Pregnancy test	X (blood) ⁴	X (urine) ⁵						X (urine) ⁵					X (urine)	X (urine) **
Physical examination	X ⁴							X ⁷					X	X ⁸
Body weight and body surface area	X	X ⁹						X ⁹					X	
Vital signs	X	X ¹⁰	X ¹⁰	X ¹⁰	X ¹⁰	X ¹¹		X ¹⁰	X ¹⁰	X ¹⁰	X ¹¹		X	X ⁸
Hematology¹²	X	X ⁶	X ⁵	X ⁶	X ⁵	X ⁵		X ⁶		X ⁶		X ⁵	X	
Biochemistry¹²	X	X ⁶	X ⁵	X ⁶	X ⁵	X ⁵		X ⁶		X ⁶		X ⁵	X	
Coagulation¹²	X	X ^{6,13}		X ⁶		X ⁵		X ⁶				X ⁵	X	
Urinalysis	X ⁴							X ¹¹					X	
Creatinine clearance	X	X ¹¹						X ¹¹						
Electrocardiography	X	X ¹¹						X ¹¹					X	
Echocardiography/multiple gated acquisition scanning	X													

Cycle	Visit	Screening Up to 21 days before day 1 of cycle 1	Cycle 1					From cycle 2 onwards					End of treatment* Within 7 (+7) days after the last dose of nanrilkefusp alfa and/or cetuximab (whichever occurs later)	Follow -up
			Day 1	Day 2 (±1 day)	Day 8 (±1 day)	Day 9 (±1 day)	Day 15 (±1 day)	Day 1 (±1 day)	Day 2 (±1 day)	Day 8 (±1 day)	Day 9 (±1 day)	Day 15 (±1 day)		
Eastern Cooperative Oncology Group performance score	X ⁴	X ¹¹						X ¹¹					X	X ⁸
Tumor assessment (CT/MRI)	X ¹⁴		Every 6 weeks (±2 weeks) starting from day 1 of cycle 1 until confirmed disease progression per iRECIST, start of next-line anti-cancer treatment, pregnancy of the patient, withdrawal of consent by the patient, or end of the study											
Nanrilkefusp alfa administration ¹⁵		X	X	X	X			X	X	X	X			
Cetuximab administration ¹⁶		X		X		X		X		X		X		
Adverse events	X		X											X ^{8,17}
Concomitant medication/ non-drug therapies	X		X											X ^{8,17}
HIV, hepatitis B and C	X													
Serum for nanrilkefusp alfa pharmacokinetics			See Table 1.1											
Serum for nanrilkefusp alfa anti-drug antibodies		X ¹¹						X ^{11,18}						X ⁸
Serum for cetuximab pharmacokinetics			See Table 1.1											
Serum for cetuximab anti-drug antibodies		X ¹¹						X ^{11,18}						X ⁸

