Serum for cytokines		X ¹⁹						X ^{19,20}						
Whole blood for exploratory biomarkers		X ^{11,21}						X ¹¹						
Survival status														X ²²
Next-line anti-cancer treatment														X ²²
Date of progression on next-line anti-cancer treatment														X

- * Criteria for discontinuation of study interventions are listed in section [7.1](#).
- ** Every 30 (± 2) days until 60 (± 2) days after the last dose of cetuximab or 30 (± 2) days after the last dose of nanrilkefusp alfa, whichever is later
- 1. No study-specific procedures are to be performed before Informed Consent Form signature
- 2. Age at screening and gender
- 3. Primary tumor location, histology/cytology, initial diagnosis date, lines of previous treatment, start and stop dates of the treatments before this study, any prior mutations/genetic analysis (e.g., EGFR, K-RAS/N-RAS mutations), and the date of the latest disease progression if not coinciding with the stop date
- 4. Within 7 days before day 1 of cycle 1
- 5. On the day of dosing before nanrilkefusp alfa administration and/or cetuximab administration
- 6. Sample can be taken within 24 hours before nanrilkefusp alfa and/or cetuximab administration
- 7. Before nanrilkefusp alfa administration and afterwards as clinically required
- 8. Follow-up visit 30 (± 2) days after the last dose of nanrilkefusp alfa and/or cetuximab (whichever occurs later)
- 9. Last body weight assessment within 3 days prior to day 1 should be used for dose calculation.
- 10. Before and after nanrilkefusp alfa administration as described in section [8.2.3](#)
- 11. Before nanrilkefusp alfa and/or cetuximab administration
- 12. Additional samples may be taken as clinically indicated
- 13. Before nanrilkefusp alfa administration and 2 hours (± 15 min) after nanrilkefusp alfa administration
- 14. Tumor scans performed as part of routine clinical management are acceptable for screening if they are of acceptable diagnostic quality and performed within 21 days prior to ICF signature
- 15. Time to be recorded
- 16. Time to be recorded; on day 1 and day 8, cetuximab infusion will start within 30 minutes after nanrilkefusp alfa administration
- 17. Contact 90 (± 2) days after the last dose of nanrilkefusp alfa and/or cetuximab (whichever occurs later)
- 18. To be collected up to cycle 4
- 19. Before nanrilkefusp alfa administration and 6 hours (± 15 min) after nanrilkefusp alfa administration
- 20. Only in cycle 2

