9.3 Statistical analyses

9.3.1 General considerations

Analyses will be descriptive (i.e., without a comparison). Safety will be analyzed as described in section [9.3.3.2](#).

Summary statistics will include:

- Counts and percentages (categorical data)
- Number of observations, mean, standard deviation, median, minimum, and maximum (continuous data)

The ORR, iORR, BOR, iBOR, CBR, and iCBR will use the exact method based on the binomial distribution²⁶ to derive 95% confidence intervals (CIs). Kaplan-Meier estimations and

estimations of median (if reached) with log-log 95% CI, Q1 (25th percentile), and Q3 (75th percentile) will be used for DoR, iDoR, PFS, iPFS, TtR, iTtR, TtP, iTtP, PFS2, and OS. In case of a confirmed response or disease progression, the date of the first tumor assessment evaluated as response or progression will be used for the time-to-event variables.

The last value of CT scan or MRI on or up to 21 days before the date of the first study treatment will be used as the baseline value for each assessment. Only tumor assessments prior to or at the date of initiation of further-line therapy and using CT scan or MRI will be used for the evaluation of tumor response.

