4.1.2. Screening Period

For all patients, the screening period is defined as the period from time of signing ICF to the first dose of treatment (nanrilkefusp alfa or cetuximab) (before day 1 of cycle 1). For some variables, data from more than one assessment within the screening period can be collected prior to the first dose of treatment (nanrilkefusp alfa or cetuximab).

The baseline value is defined as the last non-missing value collected before the first dose of study treatment (nanrilkefusp alfa and/or cetuximab) in the screening period. However, for K-RAS and N-RAS parameters as well as eGFR mutation status which come from Biopsy performed within 3 months prior to first dose will also be considered as baseline values.

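### The initial scan is timed from consent but the tumour baseline from first dose, so a scan that complies with Protocol 8.1.1 can be up to 42 days old and fail the 21-day baseline rule

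*Protocol*

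**What the plan says.** Two anchors are in use for the same scan.

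- **Consent.** Protocol 8.1.1: "Initial tumor scans must be performed within 21 days prior to ICF signature". Footnote 14 of the schedule (Protocol 1.3) makes routine-care scans "acceptable for screening if they are of acceptable diagnostic quality and performed within 21 days prior to ICF signature".
- **First dose.** The screening column of the same schedule, which holds the tumour-assessment entry, is headed "Up to 21 days before day 1 of cycle 1". Protocol 9.3.1 defines the baseline as "The last value of CT scan or MRI on or up to 21 days before the date of the first study treatment", and the synopsis repeats this.

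Protocol 4.1.4.1 allows up to 21 days of screening between consent and day 1 of cycle 1.

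The SAP does not restate the scan-specific rule. SAP 4.1.2 gives one baseline definition for all variables: "the last non-missing value collected before the first dose of study treatment (nanrilkefusp alfa and/or cetuximab) in the screening period". It also fixes when that period opens: "the screening period is defined as the period from time of signing ICF to the first dose of treatment". The only exception it makes begins "However, for K-RAS and N-RAS parameters as well as eGFR mutation status which come from Biopsy performed within 3 months prior to first dose" and does not mention scans. SAP section 6, which lists departures from the protocol's analyses, has no entry on the tumour baseline.

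**The concern.** A site can do exactly what 8.1.1 requires and still supply a scan that the protocol's own analysis rule does not accept as baseline. The reverse also occurs. A scan taken during screening fits the schedule column, 9.3.1 and SAP 4.1.2, but not the mandatory wording of 8.1.1. Footnote 1 of the schedule bars study-specific procedures before consent, so only a routine-care scan can meet 8.1.1 as written.

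At stake is the reference value for tumour change. For a patient whose only pre-dose scan is outside the baseline window, the absolute and percent change summaries and the waterfall and spaghetti plots in SAP 5.5.6.5 have no qualifying denominator.

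There is also an open question about the time-to-event endpoints. SAP Tables 5 and 6 (Protocol Tables 9.2 and 9.3) have a row for an incomplete or absent baseline tumour assessment, which censors PFS, iPFS, TtP and iTtP on the first day of treatment. TtR and iTtR have their own clause for a missing baseline. The plan does not say whether a scan that exists but is too old belongs there. In a single-arm study of about 52 patients, that should not be left to programming after the data are in.

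**Working it through.** No sample size, power or alpha figure in the plan depends on this point, so there is no stated figure to reproduce. The check is date arithmetic.

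**Inputs**

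- g = days from scan to consent, 0 to 21 (Protocol 8.1.1, footnote 14)
- d = days from consent to first dose, 0 to 21 (Protocol 4.1.4.1)
- Baseline window = 21 days before first treatment (Protocol 9.3.1, synopsis)

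**Scan age at first dose** = g + d.

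Maximum: 21 + 21 = 42 days. Excess over the window: 42 − 21 = 21 days. If screening is counted as ending the day before day 1, the maximum is 41, and the conclusion is the same.

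**When does a scan that complies with 8.1.1 fail 9.3.1?** When g + d > 21, that is, when g > 21 − d:

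| Screening length d | Scans outside 9.3.1 (days before consent, g) |
|---|---|
| 7 | 15 to 21 |
| 14 | 8 to 21 |
| 21 | 1 to 21 |

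So the mismatch is not confined to the extreme case. With a two-week screening period, a scan taken 8 or more days before consent is already too old.

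**Scan taken after consent.** Its age is at most d, and d ≤ 21, so it always meets 9.3.1 and falls in the SAP 4.1.2 screening period.

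**SAP 4.1.2 read literally.** Any scan with g ≥ 1 predates the screening period and is left out, whatever d is. For example, with g = 5 and d = 7 the scan is 12 days old. It meets 9.3.1 but not the literal SAP definition.

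These are conditions on dates. They are not shares of patients.

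**Do other passages resolve it?**

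- Protocol section 8 accepts routine procedures done before consent for baseline use if they fall within the schedule's time frame. The schedule carries both anchors, so this returns the question unanswered.
- SAP 4.1.4 analyses data by nominal visit, but its tumour windows begin at week 6 and none is given for baseline.
- SAP 5.5 carries over two neighbouring rules from 9.3.1 (dating from the first qualifying assessment, and CT or MRI before further-line therapy) but not the 21-day baseline sentence.

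**Which endpoints depend on it?** SAP 5.5 maps RECIST 1.1 response from the response assessment form, so ORR does not use the baseline window. The same form supplies progression, so PFS and TtP change only if the day-1 censoring row is applied.

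**The case against.** **The SAP definition is generic.** SAP 4.1.2 covers all variables and never mentions scans, whereas 9.3.1 is written specifically for CT and MRI. With no departure listed in SAP section 6, the natural reading is that 9.3.1 still governs. A reader might infer from SAP 4.1.2 that every scan before consent is disqualified. The documents do not support that as the intended rule, because it needs a general sentence to override a specific one silently. The objection stands to this extent: the SAP part is a wording gap, and the firm conflict is between 8.1.1 and 9.3.1. It does not rescue scans 22 to 42 days old, which fail 9.3.1 itself.

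**8.1.1 may be a slip.** Its next sentence speaks of screening scans, and the schedule places the assessment in the screening column. That is plausible, but the wording is mandatory, footnote 14 repeats the anchor, and Protocol section 8 rules out waivers. It needs correcting either way.

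**The impact is limited.** A reader might also infer that affected patients will be censored on day 1 for PFS and TtP. That is a possible reading and not a stated rule. The tables are introduced for patients with missing data, the row describes an absent or incomplete assessment and not an old one, and Protocol 5.1 requires a measurable lesion, so an enrolled patient should have a scan. The tumour-burden outputs that are directly affected are exploratory, and the trial is descriptive. All of this stands and keeps the point modest.

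**Other documents may settle it.** The site imaging manual and the eCRF were not available. The absence of a fallback rule is shown only for the protocol and SAP.

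**Conclusion.** The conflict holds, and it should be fixed. Following 8.1.1 as written can produce a scan up to 42 days old at first dose against a 21-day baseline window. If there is no later pre-dose scan, the patient has no qualifying tumour baseline under 9.3.1. The literal SAP 4.1.2 wording adds an ambiguity for younger scans taken before consent, though 9.3.1 probably prevails.

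The direct effect is confined to the change-from-baseline summaries and the waterfall and spaghetti plots. For PFS, iPFS, TtP and iTtP the effect is conditional on how the no-baseline row is applied. It would be wrong to infer any threat to the primary endpoint: ORR comes from the response form and is not affected.

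The number of patients cannot be estimated from the documents. It is zero if every patient has a scan during screening. The 42-day figure assumes that both 21-day windows are fully used.

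**What to change.** 1. Reconcile Protocol 8.1.1, footnote 14, the schedule column and 9.3.1 with the synopsis to one anchor, so that any scan meeting the timing rule also meets the baseline rule. The choice of anchor is the sponsor's. The statistical requirement is only that the two rules agree.
2. Add to SAP 4.1.2 that the tumour baseline is the most recent CT or MRI before first dose under the reconciled rule, whether taken before or after consent. List this in SAP section 6.
3. State that a patient whose only pre-dose scan falls outside the window keeps that scan as the reference value and is flagged. Such a patient is not treated as having no baseline in SAP Tables 5 and 6 (Protocol Tables 9.2 and 9.3) or in the missing-baseline clause for TtR and iTtR.

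Defining the baseline as the most recent pre-dose scan keeps the principle in 9.3.1 and avoids preferring an older eligibility scan over a newer one.

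The cost is a few sentences in the SAP and wording edits to the protocol, made together so that they do not contradict each other. The downside is small: a few flagged baselines may be older than 21 days, and the flag makes them visible.
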